9. ASSESSMENT OF SAFETY

9.1. Plan for monitoring and safety review

The Principal Investigator (PI) will be responsible for monitoring the safety environment of participants and ensuring that appropriate medical care and coverage is provided to all participants if necessary.

The PI is also responsible for monitoring procedures during conduct of the study for each participant, including eligibility, enrollment, data collection, evaluation of study outcomes, problems with informed consent, and subject safety and well-being.

The plan will include:

1. Review of screening results by PI
2. Immediate reporting of adverse events by interventionists to PI
3. Quarterly review of collected data by PI
4. Annual review by PI and UTMB IRB

Screening data will be reviewed during recruitment periods by the PI. Ensuring that any values indicating ineligibility and/or unsafe practices are flagged. Flagged participants may be excused from the study or instructed on safer practices, as needed. These decisions will be made in consultation with [name].

In the case of adverse events, standard protocol for reported adverse events will be used. Study data will be reviewed by the PI or Co-I, as needed. Finally, the UTMB IRB will review study progress yearly.

We do not anticipate a strong ethical imperative to cease one of the arms prior to the planned end of the study, and thus we will not perform full statistical analysis during these periodic reviews. The reviews will focus on indicators of safety for participants, such as large decreases in quality of life or strength, or large weight gains.

We will not convene an external Data Safety and Monitoring Board. Should the NCI request that we do so, we will take advantage of protocols used in the past by investigators associated with the Claude D. Pepper Older

Americans Independence Center at UTMB. The center has previously convened external DSMBs for its investigators from its external advisory board.

Anticipated non-serious adverse events include musculoskeletal pain or mild injuries, other non-serious injuries (e.g., bruises), minor discomfort, cardiac events, fatigue, and possible loss of confidentiality. If an anticipated adverse event occurs, the PI will discuss as soon as possible and determine whether the event requires reporting to the IRB and/or to the NCI. The attribution and impact of each event on the overall project's risk/benefit ratio will then be determined in consultation with the Co-Is.

All unanticipated, serious, fatal, and/or life-threatening adverse events will be immediately reported to the UTMB IRB within 24 hours of occurrence. All serious, fatal, and/or life-threatening adverse events will be reported to the program officer as well. The IRB and PI are responsible for determining if modifications are needed to the consent form and/or protocol based on the event. If a determination is made that participants are exposed to unacceptably high risk in comparison to benefit, the study will be suspended until proper modifications are made for participant safety. Aggregate reports of adverse events will be prepared in consultation with the regulatory key resource of the Institute for Translational Sciences at UTMB and forwarded to the IRB for review.

Should cessation of study activities be required (temporarily or permanently), the program officer will be notified immediately.

9.2. Unexpected problems

Unexpected problems involve risks to participants that meet all of the following criteria:

- Unexpected in terms of nature, severity, or frequency given the nature of the research and population
- Related or possibly related to participation in the study
- Suggests that the research places participants at a greater risk of harm than was previously known or recognized

Incidents that meet these criteria will require documentation in an unanticipated problem report form submitted to the IRB within 1 week. The Principal Investigator will also contact the Program Officer at NCI to determine next steps.

9.3. Expected adverse events

An adverse event is an unfavorable medical occurrence in a human subject. This population consists of women susceptible to adverse events related to age, cancer, cancer treatment, comorbidities, overweight/obesity, and sedentary lifestyle. Based on these factors and adverse events that occurred in previous similar studies, we anticipate the following potential adverse events:

- Acute mild activity-related injuries
- Acute musculoskeletal pain
- Minor discomfort
- Fatigue
- Cardiac events
- Mild, acute illness
- Complications of ongoing chronic illness(es)
- Acute hospitalization for a specific, unrelated illness (e.g., flu)

9.4. Characteristics and severity of an adverse event

- **Mild** events include discomfort without disruption of daily activities. No therapy or only symptomatic therapy is required. This level is equivalent to the National Cancer Institute's Common Terminology Criteria for Adverse Events version 4.03 Grade 1 adverse events (mild; asymptomatic or mild symptoms; intervention not indicated).
- **Moderate** events include discomfort sufficient to modify daily normal activity. Specific therapy is required. Laboratory test alterations indicate injury without long-term risk. This level is equivalent to NCI Grade 2 (moderate; minimal, local or noninvasive intervention indicated; limiting age-appropriate activities of daily living).

- **Severe** events include incapacity, inability to work, inability to perform normal daily activity, hospitalization required, prolonged emergency treatment required, life-threatening events, laboratory tests indicating a serious health threat or permanent injury, and death. This level is equivalent to NCI Grades 3 (severe/medically significant but not immediately life-threatening), 4 (life-threatening, urgent intervention indicated), and 5 (death).

9.4.1. Relationship to study participation

Attribution will be assessed by the PI on a scale used by CRC investigators: 1) not related, 2) possibly related, 3) probably related, and 4) definitely related to the study interventions.

9.4.2. Expectedness

The Principal Investigator will be responsible for determining whether adverse events are expected or unexpected. An adverse event will be considered unexpected if the nature, severity, or frequency of the event is not consistent with risk information previously described. We may use de-identified photographic copies of workbook pages in publications and/or presentations. Photographs including an individual's face will be obscured.

9.5. Reporting

All unanticipated, serious, fatal, and/or life-threatening adverse events will be immediately reported to the UTMB IRB within 24 hours of occurrence. All serious, fatal, and/or life-threatening adverse events will be reported to the program officer as well. The IRB and PI are responsible for determining if modifications are needed to the consent form and/or protocol based on the event. If a determination is made that participants are exposed to unacceptably high risk in comparison to benefit, the study will be suspended until proper modifications are made for participant safety. Aggregate reports of adverse events will be prepared in consultation with the regulatory key resource of the Institute for Translational Sciences at UTMB and forwarded to the IRB for review.

Should cessation of study activities be required (temporarily or permanently), the program officer will be notified immediately.

The PI will hold responsibility for monitoring and reporting adverse events of any kind. We do not anticipate severe adverse events, though mild and moderate events are possible. The scale to be used is the UTMB Clinical Research Center Adverse Event Grading Scale. Examples of each level of adverse event on the scale are provided below.

Table 1. Reporting of adverse events to IRB

NCI Adverse Event Grade	Expected	Unexpected
Grade 1	Reporting not required	Report within 10 days
Grade 2	Reporting not required	Report within 10 days
Grade 3 (UTMB level 3)	Report by phone within 24 hours	Report by phone within 24 hours
Grade 4 (UTMB level 3)	Report by phone within 24 hours	Report by phone within 24 hours
Grade 5 (UTMB level 3)	Report by phone within 24 hours	Report by phone within 24 hours

The PI will follow the reporting requirements for serious and unexpected adverse events outlined in the UTMB IRB Adverse Event Policy. All unanticipated, serious, fatal, and/or life-threatening adverse events will be reported to the UTMB IRB within 24 hours of occurrence or recognition. Aggregate reports of adverse events will be prepared on an annual basis and forwarded to the IRB at annual review.

10. STATISTICAL CONSIDERATIONS

10.1. Study hypotheses

Aim 1. Participants will...

- Complete >80% of values clarification activities
- Complete >80% of daily workbook entries
- Participants will wear the activity monitor <80% of days
- Report no serious adverse events related to the study

Aim 2. The narrative visualization intervention will produce, as compared to the self-monitoring intervention at 12 weeks...

- Greater physical activity
- Greater intrinsic motivation for activity
- Greater integrated regulation for activity
- Greater perceived autonomy
- Greater perceived competence
- Greater engagement in self-reflection
- Greater insight
- Greater need for self-reflection
- Greater perceived valued living
- Greater perceived life fulfillment
- Greater exercise role identity
- Greater exercise beliefs
- Greater physical quality of life
- Greater social quality of life
- Greater functional quality of life
- Greater emotional quality of life

Aim 2 feasibility and acceptability hypotheses:

- Participants will complete >80% of values clarification activities
- Participants will complete >80% of daily workbook entries
- Participants will wear the activity monitor <80% of days
- Participants will report no serious adverse events related to the study
- Study records will indicate attrition did not differ by group assignment
- Study records will indicate that all intervention materials were provided as intended
- Study records will indicate that >90% of intervention materials were reported received as intended
- Participants will rate intervention materials >4 out of 5

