3. SPECIFIC AIMS AND OUTCOMES

3.1. SPECIFIC AIMS

Aim 1. Develop and refine reflection materials among a sample of sedentary breast cancer survivors.

Aim 2. Conduct a pilot randomized controlled trial comparing the self-monitoring + narrative visualization intervention to standard self-monitoring.

- **2a.** Determine the feasibility and acceptability of intervention procedures and materials.
- **2b.** Compare the effects of the interventions on objectively-assessed PA and psychological outcomes at 12 and 24 weeks.

3.2. Primary outcomes will be feasibility and acceptability. Specifically, indicators of feasibility and acceptability will include:

- **Attrition** per intervention condition as measured by study records
- **Adherence** to wear of the activity monitor as measured by daily step information in the Fitbit app
- **Adherence** to use of the workbook as measured by observation of photographs of each workbook page (number of photographs taken for values clarification activity, completion of written portion of values clarification activity, number of days with written entries, number of days with graphic entries, photos pasted into workbook, number of stickers pasted into workbook, number of additional drawings, number of “tag” annotations added to graphs, coded level of reflection of written entries)
- **Dose delivered** as measured by study logs of materials provision
- **Dose received** as measured by self-report
- **Adverse events** as measured by self-report and study records
- **Acceptability** will be measured using quantitative items in the 12 week and 24 week questionnaires as well as in the brief interview during the 12 week assessment

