10.3.2. Quantitative

All quantitative analyses will be performed by the study statistician, who will be blinded to group allocation. For tests of feasibility and acceptability, we will use descriptive statistics only.

A priori benchmark indicators will be used from a variety of similar studies (e.g., 80% completion, no serious related adverse events) to indicate whether feasibility or acceptability were achieved.

For quantitative hypotheses, we will use analyses of covariance, controlling for baseline values of the dependent variable as well as time since diagnosis. We will follow the intent to treat principle, and imputation methods will be used as necessary to account for missing data. As indicated above, these outcomes will be used primarily for the purposes of shaping a fully powered follow-up study.

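### The activity-monitor wear benchmark in section 10.1 is printed with its inequality reversed, for both Aim 1 and Aim 2

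*Combined protocol and SAP*

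**What the plan says.** Section 3.2 states that "Primary outcomes will be feasibility and acceptability" and includes among the indicators adherence "to wear of the activity monitor as measured by daily step information in the Fitbit app".

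Section 10.1 then gives the benchmarks. For monitor wear the Aim 1 list reads "Participants will wear the activity monitor <80% of days", and the Aim 2 feasibility and acceptability list repeats the bullet word for word. The items around it include "Complete >80% of values clarification activities" (Aim 1), "Participants will complete >80% of daily workbook entries" (Aim 2) and "Study records will indicate that >90% of intervention materials were reported received as intended" (Aim 2).

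Section 10.3.2 says that feasibility and acceptability will be summarised descriptively and compared with benchmarks fixed in advance: "e.g., 80% completion, no serious related adverse events) to indicate whether feasibility or acceptability were achieved".

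**The concern.** An adherence benchmark should be met when adherence is high. As printed, this one is met when participants leave the monitor off. The monitor is a core element of both arms: its step data are what participants log, chart or reflect on. Nothing in the documents gives a reason to aim for low wear.

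What is at stake is the verdict on one indicator of the primary outcome. That verdict comes from setting a descriptive figure against a pre-stated cut-off, so the printed cut-off is the decision rule for this indicator. There is no test, interval or second statement of the benchmark that would catch a wrong sign. The investigators would have to choose between two bad options at reporting. They could apply the rule as written and call good wear a failure, or they could depart from it after seeing the data, which would look like a post hoc change to a primary-outcome threshold.

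**Working it through.** The benchmark is a stated cut-off, so there is no calculated figure to reproduce. The check has two parts: whether the direction fits the rest of the plan, and what the printed rule does to possible results.

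**1. Direction of the numeric feasibility benchmarks in section 10.1**

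| Item | List | Printed benchmark | High value counts as |
|---|---|---|---|
| Values clarification activities | Aim 1 and Aim 2 | >80% | success |
| Daily workbook entries | Aim 1 and Aim 2 | >80% | success |
| Materials reported received | Aim 2 | >90% | success |
| Rating of materials | Aim 2 | >4 out of 5 | success |
| Monitor wear | Aim 1 and Aim 2 | <80% | **failure** |

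Monitor wear is the only item that runs the other way, and it does so in both lists. A fault in reading the PDF is an unlikely explanation, because the greater-than signs on adjacent lines are intact and the same bullet is affected twice. Section 3.2 calls the measure adherence. Section 10.3.2 treats 80% completion as a sign of success. No section restates the wear benchmark with the opposite sign.

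**2. Effect on results**

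Inputs: the Aim 1 period is one week (7 days) with 20 women, and the RCT intervention is 12 weeks with 40 participants (Summary). The monitor is for use during the intervention period (Summary), so the RCT denominator is taken as 12 × 7 = 84 days. Applying the cut-off to each participant is an assumption, because section 10.1 does not state the unit.

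Cut-offs in days:

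- Aim 1: 0.80 × 7 = 5.6 days
- RCT: 0.80 × 84 = 67.2 days

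| Wear days | Proportion | As printed (<80%) | With the sign corrected (>80%) |
|---|---|---|---|
| 0 of 7 | 0% | met | not met |
| 4 of 7 | 57.1% | met | not met |
| 6 of 7 | 85.7% | not met | met |
| 7 of 7 | 100% | not met | met |
| 0 of 84 | 0% | met | not met |
| 42 of 84 | 50.0% | met | not met |
| 67 of 84 | 79.8% | met | not met |
| 68 of 84 | 81.0% | not met | met |
| 80 of 84 | 95.2% | not met | met |
| 84 of 84 | 100% | not met | met |

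Every row reverses. As printed, 0 to 5 of 7 days and 0 to 67 of 84 days meet the criterion, while 6 or 7 days and 68 to 84 days fail it.

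**3. Dependence on the unit**

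The reversal does not depend on the per-participant reading. A group mean or a pooled proportion of days also passes below 80% and fails above it. The unit matters only at exactly 80%. One participant cannot land there, since 5.6 and 67.2 are not whole days. Pooled days could: 0.80 × (20 × 7) = 112 of 140 in Aim 1, and 0.80 × (40 × 84) = 2,688 of 3,360 in the RCT. At that point either strict inequality fails.

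**The case against.** The strongest reply is that this is an evident typing error which the document itself resolves. The word adherence, the neighbouring items and section 10.3.2 all show the intended direction, and a careful analyst would be unlikely to report 95% wear as a failure. The observed wear percentage would be reported whichever sign is printed. Wear is one of several indicators, and no rule says that one missed benchmark decides overall feasibility. The only explicit rule for proceeding, in section 10.2, concerns integrated regulation.

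Most of this is fair, and it limits the consequence: a wrong conclusion follows only if the rule is applied as written, and overall feasibility does not rest on this item alone. It does not make the printed criterion correct. A benchmark set in advance exists so that nobody has to infer the pass rule after seeing the data, and no correct restatement is available to fall back on.

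Two narrower points also stand. The fault is an internal inconsistency rather than a miscalculation. And the plan does not say whether 80% applies to each participant, to a group mean or to pooled days, nor what counts as a Fitbit wear day; the 10-hour, 4-day validity rule in section 3.3 is for the Actigraph. Correcting the sign leaves those gaps open.

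**Conclusion.** The concern holds. The monitor-wear benchmark is reversed in both lists of section 10.1, and it must be corrected because it is the stated criterion for an indicator of the primary outcome. Its pass or fail verdict is wrong for every result other than exactly 80%, in both phases (20 + 40 = 60 participants).

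The 67/68-day and 5/6-day splits assume a per-participant cut-off over 84 and 7 days; the reversal itself needs no such assumption. That the intended direction is above 80% is an inference from the sibling items and section 10.3.2, but the documents offer no competing reading. Sample size, power and the progression rule in section 10.2 are not affected.

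**What to change.** In both bullets of section 10.1, replace the less-than sign with a greater-than sign, so that the benchmark is wear on more than 80% of days, and record the correction as an amendment. The strict sign matches the sibling items; if the sponsor prefers at least 80%, the text should say so.

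It would help to add, in the same amendment, one sentence giving the unit of the benchmark (per participant, group mean or pooled days), the denominator period and the definition of a Fitbit wear day.

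The correction is two characters and does not affect data collection, operations or sample size.

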10.2. Sample size considerations

As a Phase Ia evidentiary study, hypothesis tests are not powered to detect statistical significance. A study of 40 individuals would have 80% power to detect a large effect size of approximately $F = 0.45$ for an ANCOVA model, but we will not interpret statistical significance. Rather, we have set a priori cut points for effect sizes to which we will compare our outcomes. These effect sizes represent points at which we can conclude that the intervention components adequately impact psychosocial and behavioral outcomes to proceed to further testing. For the comparison to the standard group, the intervention group must produce at least a small effect size difference in integrated regulation to allow us to proceed to Phase Ib.

10.3. Final analysis plan

10.3.1. Qualitative analyses

Qualitative investigations of interview transcripts and workbook content will be performed using NVivo. We will use thematic analysis to create codes to better understand how participants reacted to specific aspects of the intervention.³⁷

Interviews will be recorded and transcribed with interviewer field notes, then the investigators will refine any materials or procedures that were flagged by participants. Once the investigators have come to a consensus, we will apply insights from this sub-study to orientation procedures and intervention materials as needed.

We will use Fleck's procedures for coding reflection levels in the workbook text.³⁸ These procedures involve creating "chunks" of content surrounding a particular theme, then rating these chunks against a framework of reflection levels. We will count the number of instances of each level of reflection within the text workbook responses. Artistic content will be analyzed using standard thematic analysis, as Fleck's procedures investigate reflective text or verbal responses to art rather than reflection in the art itself.

10.3.2. Quantitative

All quantitative analyses will be performed by the study statistician, who will be blinded to group allocation. For tests of feasibility and acceptability, we will use descriptive statistics only.

A priori benchmark indicators will be used from a variety of similar studies (e.g., 80% completion, no serious related adverse events) to indicate whether feasibility or acceptability were achieved.

For quantitative hypotheses, we will use analyses of covariance, controlling for baseline values of the dependent variable as well as time since diagnosis. We will follow the intent to treat principle, and imputation methods will be used as necessary to account for missing data. As indicated above, these outcomes will be used primarily for the purposes of shaping a fully powered follow-up study.

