1. SUMMARY

Women breast cancer survivors are at increased risk for several negative health outcomes. Physical activity can reduce these risks, but activity levels in this population are low. Standard interventions that use self-regulation techniques (goal setting, self-monitoring, and feedback) are successful in the short term but do not produce the long-term activity maintenance needed for optimal health benefits. Their effectiveness might be improved by better connecting activity feedback to individuals' real-life experiences and values. Integrated regulation is a form of motivation related to personal values and identity and is strongly related to physical activity over time. Increasing this form of motivation could improve upon current intervention strategies, particularly in this population. Narrative visualization uses photographic, visual, and text annotation to tell a meaningful story with a data chart. This form of visualization can increase reflection, which in turn can predict integrated regulation and physical activity. We hypothesize that an intervention that encourages participants to create narrative visualizations from their step self-monitoring data will produce greater increases in physical activity than a self-regulation intervention. To test this hypothesis, we must first investigate the feasibility and acceptability of the narrative visualization intervention in a pilot randomized controlled trial. We will recruit 60 women breast cancer survivors (aged 55 – 79, < 150 minutes of physical activity per week) in two phases. In Phase I, 20 women will use prototype materials for one week and undergo cognitive interviewing to investigate feasibility and acceptability. Materials will be revised based on responses for use in the subsequent trial. In Phase II, we will randomize 40 participants to receive either the narrative visualization intervention or a standard self-regulation intervention for 12 weeks (with 12 weeks of no-intervention follow-up). Both groups will receive a wearable activity monitor and feedback app for use during the intervention period as well as an initial orientation/goal setting meeting and workbook. In the self-regulation group, participants will receive a workbook in which they will write and log their weekly goals. The narrative visualization group will also receive extended workbook content, a photo printer, and art supplies. The expanded workbooks will include spaces for posting daily photos and drawing explanations of step charts as well as reflection prompts relating the photos and charts to personal values and identity. Participants will be assessed at baseline, 12 weeks, and 24 weeks on changes to their activity, reflection, and integrated regulation. Feasibility indicators will include wear of the monitor and usage of the workbooks. Results from this study will be used to refine the intervention and to develop a follow-up study powered to investigate the relationships between reflection, motivation, and activity. Our overarching goal is to reduce the burden of cancer and improve quality of life among breast cancer survivors. This project represents a critical step towards this goal. Insights from the study will impact research and practice by testing a highly novel, scalable, and motivating intervention in a population at unique risk.

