4. STUDY DESIGN

This study will combine an initial formative, qualitative study with a pilot randomized controlled trial. The target population is breast cancer survivors aged 55 – 79 who are sedentary (< 150 minutes of physical activity per week), and who completed their primary cancer treatments at least 6 months prior to enrollment. This trial corresponds approximately to phases Ib (formative research to refine the intervention) and IIb (pilot randomized controlled trial to investigate feasibility and effect sizes) in the ORBIT model of behavioral intervention development. The trial itself will occur at a single center, but recruitment will occur at both UTMB and MD Anderson.

We anticipate that the duration of the Aim 1 phase will be approximately four months. From the beginning of recruitment to the final data collection point, we expect the trial to take one year to complete. The trial will consist of two arms: the narrative visualization intervention condition and an attention control intervention that includes only standard self-monitoring.

5. Study enrollment and withdrawal

5.1. Inclusion criteria for Aim 1

1. Age between 55 and 79
2. Female
3. Self-reported diagnosis of breast cancer
4. Participant is inactive (reports less than 150 minutes of moderate-vigorous intensity activity per week)
5. Able to read and understand English
6. Daily access to a smartphone or similar device compatible with Garmin or Fitbit app

5.2. Exclusion criteria for Aim 1

No exclusion criteria for the Aim 1 study will be used.

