5.7. Randomization

A random number generator will be used to create a list of group assignments by ID number. Sheets containing group assignments (intervention or comparison group) will be placed in envelopes that are labeled with the corresponding ID number. The envelopes will be opaque, and foil will be placed inside to ensure that the randomizer cannot see inside. Carbon paper will also be included to provide an audit trail. ID numbers will be assigned in the order participants arrive to their randomization visit. Upon opening the envelope, the staff member undertaking the randomization will sign and write the date on the envelope. The inner paper that lists the group assignment, with the ID, signature, and date written on it via carbon paper, will be kept in the participant's file.

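### The primary feasibility benchmarks are judged achieved or not without intervals, and the plan gives no precision basis for them at about 20 women per arm

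*Combined protocol and SAP*

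**What the plan says.** Section 3.2 states: "Primary outcomes will be feasibility and acceptability". The Aim 2 feasibility list in section 10.1 gives the cut-offs. Two of them read "Participants will complete >80% of daily workbook entries" and "Participants will report no serious adverse events related to the study". The others are:

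- more than 80% of values clarification activities completed
- a monitor-wear percentage of days
- no difference in attrition between groups (no margin given)
- all materials provided
- more than 90% of materials reported as received
- a rating above 4 out of 5

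Section 10.3.2 sets the method: "For tests of feasibility and acceptability, we will use descriptive statistics only". It then says that the benchmarks will be used "to indicate whether feasibility or acceptability were achieved".

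On size, the Summary says: "In Phase II, we will randomize 40 participants to receive either the narrative visualization intervention or a standard self-regulation intervention for 12 weeks". Section 4 adds: "The trial will consist of two arms". Section 5.7 gives no allocation ratio and no blocking: "A random number generator will be used to create a list of group assignments by ID number". The only sample-size figure, in section 10.2, is 80% power at an ANCOVA effect size of about 0.45. The same section says that statistical significance will not be interpreted.

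**The concern.** The plan turns estimates into a verdict of achieved or not achieved, but does not say how precise they will be. The one numerical justification of the sample size concerns secondary comparisons. For the primary outcomes there is no interval, no target precision and no statement of what 20 women can show.

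If the true completion rate is near a cut-off, sampling variation alone can put the observed figure on either side. A report that gives only the observed percentage and the word achieved would not let a reader see this. The Summary says that the results will be used to refine the intervention and to develop the follow-up study, so the strength of the feasibility evidence matters.

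**Working it through.** **Inputs.** From the documents: 40 women randomised, two arms, cut-offs as in section 10.1. Assumed: equal allocation, so n = 20 per arm; two-sided 95% intervals; between-woman SD of 10 to 30 percentage points for the share of entries or days (the documents give no SD).

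**1. The plan's own figure.** Noncentral F test, 1 numerator degree of freedom, two covariates, denominator df = 40 − 2 − 2 = 36, noncentrality 40 × 0.45² = 8.1, two-sided alpha 0.05 (assumed). Power is 79.1%. The stated 80% is reproduced, but it says nothing about the feasibility benchmarks.

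**2. Benchmark read as a mean percentage over women.** This is the natural reading, because section 10.1 counts entries, activities and days. Half-width = t(0.975, n − 1) × SD/√n, with t = 2.093 for n = 20 and 2.023 for n = 40.

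| Assumed SD (points) | Half-width, n = 20 | Half-width, n = 40 | Chance of wrong side of 80%, truth 5 points away, n = 20 |
|---|---|---|---|
| 10 | 4.7 | 3.2 | 1% |
| 15 | 7.0 | 4.8 | 7% |
| 20 | 9.4 | 6.4 | 13% |
| 25 | 11.7 | 8.0 | 19% |
| 30 | 14.0 | 9.6 | 23% |

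The last column is Φ(−5 / (SD/√20)). For SD 20, SD/√20 = 4.47 and Φ(−1.12) = 0.13.

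**3. Benchmark read as a proportion of women.** The plan does not define this reading, but does not exclude it. Clopper-Pearson 95% intervals:

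- 16/20 (80%): 56.3% to 94.3%
- 17/20 (85%, the smallest count above 80%): 62.1% to 96.8%
- 32/40 (80%, both arms pooled): 64.4% to 90.9%

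With Binomial(20, p), the chance of 17 or more is 22.5% at a true 75%, 41.1% at 80%, 64.8% at 85% and 86.7% at 90%.

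**4. Rating above 4 of 5.** With an assumed SD of 0.5 to 1.0 and n = 20, the half-width is 2.093 × SD/√20 = 0.23 to 0.47 points.

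**5. Attrition difference.** Illustration: 2/20 against 4/20 differs by 10 points. The Wald half-width is 1.96 × √(0.1 × 0.9/20 + 0.2 × 0.8/20) = 1.96 × 0.112 = 0.22, that is, 22 points.

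**6. Zero related serious events.** One-sided 95% upper bound = 1 − 0.05^(1/n): 13.9% for n = 20 and 7.2% for n = 40. A true rate of 5% gives no events in 20 women with probability 0.95²⁰ = 36%.

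**The case against.** Descriptive analysis is normal in a pilot of this size, and no hypothesis test is needed. That stands. The planned wording does not forbid intervals either. But none is planned, and section 10.3.2 uses the estimates to reach a verdict.

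The size of the problem depends on undefined quantities. This also stands. No section classes a woman as adherent or not, so the 56% to 94% interval belongs to a secondary reading. On the reading by entries or days, the SD is an assumption. With an SD near 10 points, or a true rate far from the cut-off, the risk of a wrong verdict is small. It is therefore not established that the plan would often call a feasible intervention infeasible.

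Three stronger readings are tempting, and the documents support none of them:

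- *Sampling error could overturn the trial's main conclusion.* The only explicit criterion for moving on, in section 10.2, is at least a small effect on integrated regulation. The benchmarks are several, they sit beside interviews and thematic analysis, and no text lets one of them decide overall feasibility.
- *Zero events would be taken as proof of safety.* Zero related serious events is one feasibility benchmark. Safety is handled by the review, attribution and reporting procedures of section 9.
- *A benchmark should count as met or missed only when its whole interval lies on one side.* For proportions of women at n = 20 and an 80% cut-off, that rule needs 20/20 for met and 11/20 or fewer for not met. It would return uncertain 88% to 98% of the time for true rates of 70% to 90%. Nor does it fit the attrition comparison, which has no margin, or the target that all materials are provided.

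**Conclusion.** The concern holds in a limited form. The plan judges its primary outcomes against sharp cut-offs, with no interval and no precision basis. At about 20 women per arm, a mean completion percentage within about 5 to 14 points of its cut-off may not separate met from missed. The range corresponds to assumed SDs of 10 to 30 points. If the benchmark were a proportion of women, the uncertainty would be wider: 56% to 94% at 16/20.

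This affects the feasibility verdict and how it is reported, not the integrated-regulation criterion. The figures rest on equal allocation and complete data. Section 8.5 records that many follow-up assessments scheduled after March 2020 were missing, so fewer women may be evaluable for some benchmarks and precision would then be lower. For benchmarks that apply to all 40 women, pooling would narrow the intervals, but the plan does not say whether the arms are pooled. The values activity is given only in the narrative arm, so pooling cannot help there.

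**What to change.** In section 10.3.2:

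- For each benchmark, state the unit and denominator, and whether it is judged by arm or pooled.
- Report each completion, receipt and rating benchmark with a 95% confidence interval computed over women: bootstrap or t interval for mean percentages of entries or days and for ratings, exact interval for proportions of women. Use the narrative arm only for the values activity.
- Report the attrition difference with its 95% confidence interval.
- If no related serious events occur, give the one-sided 95% upper bound (14% in 20 women, 7% in 40).
- Word the feasibility conclusion in light of these intervals. Do not require the whole interval to lie on one side of the benchmark.

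In section 10.2, state the expected precision at n = 20 and n = 40, with the assumed SD range.

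In section 10.1, the monitor-wear benchmark is written as less than 80% of days, the opposite direction to the other completion benchmarks. The two must be reconciled before wear is judged.

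The cost is wording and slightly more analysis. It needs no new data, visits or participants. The downside is that some benchmarks will be visibly imprecise.
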